Official title: A Randomized Trial Examining Plasma Exchange using the BD Catheter In an Outpatient Apheresis Unit (REPLACE)

NCT number: NCT04253756 IRB Approved date: 4/22/2020 A Randomized Trial Examining Plasma Exchange using the BD Catheter In an Outpatient AphCresis Unit (REPLACE)

PI: [name] [name], CMSRN, QIA

Faculty Sponsor: [name] MD

Co-Investigator: [name], RN

Research manager: [name] PhD

Date: 11/27/2019

Version: 1

Introduction and Purpose

Nurses and apheresis technicians caring for patients requiring therapeutic apheresis procedures (TAP) utilize a wide range of intravenous catheters to obtain the access required to perform their procedures(Kalantari, 2012), (Golestaneh & Mokrzycki, 2013). The standard of care for our facility is to use an 18-gauge apheresis needle (Medisystems®) for the access site and an 18-gauge autogard catheter for the return site. Unfortunately, there is minimal literature defining best practices for catheter size selection(Salazar et al., 2017). At UT Southwestern Medical Center, our goal is to provide peripheral therapy to reduce the need for central access, such as a medical ports or tunneled catheters(Spires et al., 2018). However, the requirement for an 18 gauge catheter for an adequate return site, at times, rules out the patient for peripheral therapy(Putensen, Leverett, Patel, & Rivera, 2017). This requires central venous access to be obtained, which can delay the start of the procedure.

The lack of scientific evidence to support the use of smaller peripheral return catheters has increased the use of implanted ports in our institution(Putensen et al., 2017). The objectives of our pilot study are patient-centered and include analyzing the safety of using smaller peripheral return catheters without increasing the risk of hemolysis.

Background and Significance

TAP treats a wide range of disease processes and, in all cases, requires inlet and return venous access to perform the procedure. The goal of TAP is to return the patient to baseline and maintain independence and function. A larger needle (18 gauge) can cause more discomfort to the patient as well as additional scarring. A smaller needle may present less discomfort and scarring to the patient. Our goal in our outpatient clinic is to minimize disruption to the patient's routine and help them maintain normal activities of daily living.

To accomplish these goals, our outpatient clinic is open Monday thru Friday offering 4 different appointment times. All patients that are referred to our clinic for TAP, first receive a vein evaluation to see if the patient is a candidate for peripheral IV therapy. At our clinic, approximately 68% of our TAP's are performed peripherally. This eliminates the risk of a central line infection and any alteration in activities of daily living, such as bathing(Kramer, 2016), (Shang, Ma, Poghosyan, Dowding, & Stone, 2014),(Keller et al., 2018; McDiarmid, 2015).

Our hypothesis, is that the 20-gauge BD Nexiva Diffusics catheter provides the same efficacy as current practice with no increase in adverse events for patients undergoing therapeutic apheresis. The results from our study will be significant because if the 20 guage needle is equally effective for TAP, it can increase the number of patients that would be candidates for peripheral therapy. Therefore, decreasing the need for central venous access, which place the patient at an increased risk of infection. Our study is a comparison of 2 types of infusion catheters. The standard of care is an 18-gauge autogard catheter (control group) which will be compared to the 20-gauge BD Nexiva Diffusics (intervention).

- P patients who require therapeutic apheresis procedures (TAP)
- I use of 20G BD diffusics catheter during apheresis
- C use of 18 G standard of care IV catheter during apheresis
- O no difference in efficacy and no increase in safety events

Concise Summary of Project

This is a randomized pilot study of TAP using the current standard of care catheter (SOC) vs the BD Nexiva Diffusics Catheter. It is a single blinded, randomized study. Data will be used to refine and power a full randomized control trial. For this study, a sample of 33 encounters in each group (total of 66 encounters). Our specific aim is to test the hypothesis that the 20-gauge BD Nexiva Diffusics Catheter provides the same efficacy and lower pain level with no increase in adverse events for patients undergoing apheresis treatments.

Randomization Procedure

After an eligible participant is consented to the study the patient will be randomized without replacement to the use of one of the two catheters. Using a random number generator, numbers between (1-66) were randomly divided into two groups: SOC Control group and BD Intervention group (Figure 1). A study identification number (SID) key will be saved on a UTSW approved secure device and only the research coordinator will have access to the SID key showing which SID coordinates with each group. This will ensure that unblinding can occur is necessary and there is a backup to randomization.

The research coordinator will have 66 randomized envelops without replacement. Half of the envelops will be assigned to 18G catheter SOC (control) and the other half be assigned to

20G BD Nexiva Diffusics catheter (intervention). The PI will be blinded, therefore the PI will pick an envelope when patients are consented and ready for treatment. Participants will be randomized after they have consented to the study. Participants' will then be randomized to one of the two groups again at each encounter (i.e., SOC visit). Inside the envelope it will tell the investigator if the patient is in the control or intervention group of the study.

To promote a more representative sample, each patient may participate a maximum of 10 times.

Study procedure:

[figure not shown]
Each enrolled patient will participate in the study will be randomized at each encounter. During each encounter the following information will be captured:

- 1. CBC
- 2. Patient discomfort

level with placement of catheter

- 3. Inlet rate
- 4. Return line pressures
- 5. Procedures alarms
- 6. Procedure total time
- 7. Post procedure sample

Treating nurse (RN) will start the TAPs procedure with one of the 2 catheters. During the intervention period, the RN will be at bedside during as it is SOC in the Apheresis unit however for the purpose of this study the RN will have the study data collection form (DCF, Appendix1). The RN will complete the pre-assessment including a pain assessment to establish pain level prior to procedure that is currently documented in the electronic medical record. The patient will be asked to self-report the pain level after the return line has been started on the visual analog scale (VAS) Scale from 0mm to 100mm "0 being the lowest/ no pain, 100mm being the highest

level of pain". The VAS scale will be used for both the SOC and intervention group to compare the pain level when starting the return line. The RN will collect a CBC before the start of the procedure which will be used in the programing of the TAP procedure. The RN will start recording the "inlet rate, return line pressures, and alarms" every 15 minutes until the procedure is completed.

Before patient disconnects, and after the completion of procedure sing the same therapeutic apheresis procedure access site, a blood sample will be drawn by the RN 2 lavender top tubes (4ml) for plasma hemoglobin test. The plasma hemoglobin test will be sent to the UTSW lab for analysis of hemoloysis and results will be sent back directly to the PI. Blood sample results will be collected by the PI or the study team in an excel spreadsheet (CRF) that will be saved on a secure drive on the UTSW campus.

Hemolysis is defined as the destruction of red blood cells which leads to the release of hemoglobin from the red blood cells into the blood plasma. Each patient will be tested for hemolysis by running plasma hemoglobin test after the procedure has finished. This will be collected in a two lavender tops (4ml) The cost for this test is covered by sponsor and because the patient has an indwelling access to venous blood there will no charge for drawing the sample.. There is no clinical suspicion that the use of the 20-gauge BD Nexiva Diffusics Catheter will increase this risk. Hemolysis will be scored dichotomously as present or absent for each encounter.

Pain is defined as any increase discomfort experienced by the patient associated with the apheresis procedure. The current standard of care is to ask the patient "are you having pain" and then ask them to rate the pain from 0 to 10. For this study, one additional question will be asked after the patient's vein has been accessed (IV catheter in place). The patient will self-report their pain using a 100 mm VAS scale. "*The VAS has been used by healthcare providers to measure the characteristics of disease severity in each patient individually*"(Klimek et al., 2017) Currently, all peripheral apheresis patients have some pain/discomfort while having a treatment, however; it is usually tolerated with minimal complaints.

Measures of Quality of Apheresis will include inlet rate, and return pressures, procedure time. These measures are all readily available in the electronic medical record (EMR) and are all currently recorded as standard of care. The inlet rate is defined as the percent of patient inlet rate divided by the maximum allowable inlet rate. Because inlet rates are different for each type of TAP has a different maximum inlet rate, this will allow standardization across procedures. The max inlet rate for Photopheresis is 50ml/sec, the max inlet for plasma exchange is 100ml/sec inlet for red blood cell exchange is 55ml/sec. In addition, the inlet rate for each participant in the intervention arm will be compared to the average of their last 5 procedures. This measure will compare the efficiency of the SOC verses the intervention.

Inclusion Criteria

- Adult (≥ 18 years old)
- Speaks and reads English
- A patient of the Apheresis clinic at UT Southwestern University Hospital and Clinics
- Scheduled to receive TAP (therapeutic plasma exchange, red blood cell exchange and extracorporeal Photopheresis) as standard of care

Exclusion Criteria

- Prisoners
- Persons under the age of 18 years
- Patient who are actively involved in chemotherapy

Sources of Research Material

There are three sources of data for this study: electronic medical record (EMR) and paper-and-pen data collection from the patient's bedside (Data Collection form), and lab results provided by the UTSW laboratory via EMR. The EMR data that will be collected will include demographic information such as: age, sex, race, ethnicity, and admission diagnosis. The paper-and pen-data collection will include the patient self-reported pain level (VAS Scale), CBC collection, procedure data (minutes, inlet rate, return line pressures and alarms) total procedure time and post procedure sample. The paper-and-pen data collection form (Appendix 1) will record data only during patients TAP's encounter. Blood sample will be obtained from a SOC line. An additional 8 ml's for blood will be drawn from the patients for research purposes. Results from the bloodwork will be provided by the UTSW laboratory via the patient's EMR.

Recruitment Methods and Consenting Process

For this study, patients will be recruited from the Apheresis Unit at UT Southwestern University Hospital and Clinics by a member of the research team. A member of the research team will screen the electronic medical record to determine a patient's eligibility. If a patient appears eligible for the study a member of the research team will discuss eligibility criteria with a member of the clinical team (nurse manger, nurse, physician, resident, fellow, social worker). The researcher will communicate with the clinical team to ensure eligibility: adult (≥18 years old), speaks and reads English, admitted to the Apheresis Unit at UT Southwestern University Hospital and Clinics at the time of consent. All patients in this study will be able to provide selfconsent (read and speak English).

When a patient is deemed eligible, a member of the research team will discuss consent and study procedures with that patient, in a place that is comfortable for the patient. After being approached by a member of the research team, patients will have up to next visit to consider participation in the study. The study team expects recruitment of 30 participants to last approximately 8 months. (Table 1)

Potential Benefits

There may or may not be a direct benefit to the participants in this study. Any additional blood test result that seems out of the norm will be shared with the nurse on duty or treating physician. We would also hope to share this with the greater research and clinical community in hopes of finding an alternative way for apheresis patients to have therapeutic apheresis procedures with less pain and no increase in adverse events.

Potential Risks

Risks associated with BD Cather:

Longer procedure time might occur if the inlet rate of the treatment is slower. The patient will be informed of this during the ICF process. With smaller catheters there's a risk of not obtaining the appropriate return rate for the patient. When the return rate is out of the SOC parameters the SOC apheresis equipment (Optia or Cellex) will alarm. If the alarm sounds 3 times the RN will decrease inlet rate by 5 ml/sec until the minimum threshold is reached (if needed), which is 50 ml/sec for plasma exchange and 35 ml/sec for RBC exchange and 20 ml/sec for photopheresis. If the alarm continues to when the minimum threshold is reached the catheter will

be replaced with the SOC 18-gauge catheter. Obtaining blood samples may cause some discomfort, feeling lightheaded, fainting, bruising, clotting, and bleeding from the site of the needle stick and, in rare cases, infection. The risks are mitigated by drawing blood from a line that has already been established as part of SOC.

There is a low risk of breach in confidentiality. Subjects will be assigned individual study identification (SID) numbers and no personal identifiers will be included in the final summary.

Patients who are randomized to the 20-guage needle group and who fail the intervention will be given the 18-guage standard of care needle. At the patient's next visit, the patient will once again be randomized. If the patient is randomized into the 20-guage needle arm and fails the intervention a second time, the patient will be removed from the study.

Procedures to Maintain Confidentiality

Study participants will be given a study identification (SID) number. Only the approved study personnel and the principal investigator have access to the database linking the SID to the patient name. This database is kept on a protected drive on a password protected computer. Paper or hard copy participant records will be kept in a locked file cabinet in a locked office. If any identifying information is transmitted, it will be done so via secure e-mail and/or dedicated fax machines.

Statistical Analysis Plan

All data will be first collected on the DCF (Appendix I) and then entered into an electronic spreadsheet (e.g., MS Excel) which will be converted to SAS v 9.4 for analysis. All statistical analyses will be performed at UTSW in a location with secure data encryption capability. Initially, the data will be summarized first using standard measures of central tendency (mean, median, standard deviation, and interquartile range) for each variable. These will be examined to support the assumption of being approximately normally distributed. Baseline characteristics will be summarized using appropriate parametric and non-parametric measures.

The primary hypothesis is that the 20-gauge BD Nexiva Diffusics catheter provides the same efficacy of current practice with no increase in adverse events for patients undergoing therapeutic apheresis. This will be examined in 2 steps. First, ANOVA will be used to explore

efficacy wherein efficacy is represented by 1) the plasma hemoglobin value, and 2) the amount of time (minutes) required to complete a TAP. Hence models will be constructed to compare the mean plasma hemoglobin values by group, and to compare the mean number of minutes to complete TAP by group. Second, ANOVA will be used to compare the mean number of adverse events subjects experience in each group (intervention vs control).

Finally, a planned secondary analysis is to examine if the percent of lumen occupied by the return catheter is associated with return pressures. The suggested standard is that a catheter occupies < 45% of the inner-lumen diameter (measured with ultrasound). Return pressures >400 mm Hg are considered problematic. Chi-square analysis will be used to explore the odds of experiencing a return pressure > 400 mm Hg when the return catheter occupies <45% of the inner-lumen diameter.

Item	Month 1-2	Month 3-6	Month 4-8	Month 9-11	Month 12-18
IRB approval	Х				
Consent/	Х	X			
Enrollment					
Randomization	Х	X	Х	Х	
Data collection	Х	Х	Х	Х	
Manuscript				Х	X
prep					
Study closeout					X

Project Timeline

Enrollment of first patient (month 1), enrollment of the last patient (month 12), completion of data analysis (month 14), and manuscript submission (month 18). The apheresis team see approximatley 3000 TAP treaments each year. Of these, approximately 1500 encounters will meet the primary inclusion criteria. We anticipate that it will take less than 1-year to complete the study.

Future directions

The intention of this pilot study is to test the 20-gauge BD Nexiva Diffusics Catheter performance and efficacy. The findings from this study will be used to provide additional preliminary data to BD to support a National Institutes of Health or Agency for Healthcare Research and Quality (AHRQ) application (pending 2017 AHRQ funding announcements). Stakeholder feedback will be provided through an optional de-identified report to all patients and families.

Presentation of data

It is anticipated that the results from this study will be presented to American Society for Apheresis at their annual convention. The results will also be summarized in a manuscript and submitted for peer-review publication to Journal of Clinical Apheresis.

Appendix 1

Patient Sticker

A Randomized Trial Examining Plasma Exchange using the BD Catheter In an Outpatient Apheresis Unit The "REPLACE" study

Date SID Procedure Type						
Instructions:	Please complete the following form except for the VAS scale. Must be completed by patient to measure the characteristics of pain severity. Please circle option that apply.					
Collect CBC	Yes	Νο				
Catheter type	18 GA BD Autogard	20 GA BD Nexiva Diffusics				
Vein diameter w/tourniquet:	Vein diameter w/o turniquet:	Vein diameter Procedure Running:				
Asses pain after return placement						
Please rate your current pain by drawing a vertical line across the bar below						

vere		Extremely Severe		
		Procedure d	ata	
tart time:				
Inlet rate	Return line pressures	Alarms	Comments	
	tart time:	tart time: Inlet rate Return line	Procedure da tart time: Inlet rate Return Alarms line	

Total Procedure time:	Procedure en	Procedure end time:		Final Inlet Volume/Blood Processed:	
Collect post proceduer Plasma Hemoglobin	Yes		No		

References

- Golestaneh, L., & Mokrzycki, M. H. (2013). Vascular access in therapeutic apheresis: update 2013. *Journal of clinical apheresis, 28*(1), 64-72.
- Kalantari, K. (2012). The choice of vascular access for therapeutic apheresis. *Journal of clinical apheresis*, 27(3), 153-159.
- Keller, S. C., Williams, D., Rock, C., Deol, S., Trexler, P., & Cosgrove, S. E. (2018). A new frontier: Central line–associated bloodstream infection surveillance in home infusion therapy. *American journal of infection control*, 46(12), 1419-1421.
- Kramer, N. (2016). Monitoring Central Line-Associated Bloodstream Infections (CLABSI) in Home Infusion. *Infusion*, 22(4), 35-44.
- McDiarmid, S. (2015). Reduce the risk of infection by reducing the need for central lines: using ultrasound guidance to establish peripheral access in patients with sickle cell disease undergoing red cell exchange apheresis. *Journal of clinical apheresis*, *30*(2), 98-99.

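### Allocation is repeated at every visit with no balance within patient, and the analysis has no patient term: precision is lost, by an amount that depends on visit pattern and within-patient correlation

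*Combined protocol and SAP*

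**What the plan says.** The Concise Summary of Project plans "a sample of 33 encounters in each group (total of 66 encounters"). The Randomization Procedure builds one list: "Using a random number generator, numbers between (1-66) were randomly divided into two groups: SOC Control group and BD Intervention group". It then describes one pool: "The research coordinator will have 66 randomized envelops without replacement", half for each catheter. Participants "will then be randomized to one of the two groups again at each encounter", and "each patient may participate a maximum of 10 times". No pairing, blocking or stratification by patient or procedure type is described. The figure in that part of the document is not shown, but the surrounding text describes a single pool.

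The recruitment section says: "The study team expects recruitment of 30 participants to last approximately 8 months". The documents give no distribution of visits per patient.

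The Statistical Analysis Plan compares mean plasma hemoglobin, mean procedure minutes and mean number of adverse events between groups by ANOVA. No term for patient or procedure type is described. Under Potential Risks, a patient who fails on the 20-gauge catheter is randomized again at the next visit, and is removed after a second failure on that catheter.

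**The concern.** A patient who returns can serve as his or her own control, but only if both catheters are used and the analysis recognises the patient. The plan secures neither. A two-visit patient has close to an even chance of drawing the same catheter twice, and then contributes no within-patient contrast. When both catheters are drawn, an ANOVA by group still leaves differences between patients in the error term.

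Those differences may be large. Three procedure types are eligible, with different maximum inlet rates. Inlet rate is standardised for this, but procedure minutes, an efficacy measure, is not. Pain is self-reported. The data are meant to help power a full trial, so an estimate of within-patient variation would be useful in itself.

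**Working it through.** **The plan's own figure.** 33 + 33 = 66. The documents give no power, effect size, standard deviation or correlation, so there is no sample-size formula to reproduce.

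**Inputs.** From the documents: 66 encounters at 33:33, 30 expected participants, at most 10 participations each. Assumed: that the 30 supply the 66 (66/30 = 2.2 each), how visits are spread, and the ICC. The even spread is 24 patients with two visits and 6 with three (48 + 18 = 66).

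**Chance of only one catheter.** For m visits this is 2·C(33,m)/C(66,m).
- m = 2: 32/65 = 0.492.
- m = 3: (32·31)/(65·64) = 0.238.
- Even spread: (24 × 0.492 + 6 × 0.238)/30 = 13.2/30 = 44%.

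**Within-patient information.** This is the sum over patients of n1·n0/m, where n1 and n0 are a patient's encounters on each catheter.
- Single pool, expected: (66 − 30) × 0.25 × 66/65 = 9.1.
- Balanced within patient: 24 × 1/2 + 6 × 2/3 = 16.0.
- Loss: 1 − 9.1/16.0 = 43%.

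**Variance of the catheter effect.** Use a random-intercept model with total variance 1 and ICC ρ. For patient i with m visits, t of them on 20 gauge, let g = ρ/(1 − ρ + mρ). Put A = Σ(m − gm²)/(1 − ρ), B = Σ(t − gmt)/(1 − ρ), C = Σ(t − gt²)/(1 − ρ). The variance is A/(AC − B²).

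Example, balanced, ρ = 0.5: A = 32 + 9 = 41, B = 16 + 4.5 = 20.5, C = 32 + 10.5 = 42.5. Variance = 41/(1742.5 − 420.25) = 0.0310.

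Single-pool values are averages over simulated 33:33 allocations; ratios move by about one percentage point between runs. Even spread:

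| ICC (assumed) | Single pool, group means only | Single pool, patient term | Balanced, patient term | Excess (column 3 over column 4) |
|---|---|---|---|---|
| 0.1 | 0.0605 | 0.0598 | 0.0550 | 9% |
| 0.3 | 0.0602 | 0.0542 | 0.0432 | 25% |
| 0.5 | 0.0599 | 0.0439 | 0.0310 | 42% |
| 0.7 | 0.0597 | 0.0293 | 0.0187 | 57% |

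At ICC 0.5 the patient term alone, with the existing list, cuts the variance by 1 − 0.0439/0.0599 = 27%. Balance then cuts the remainder by 1 − 0.0310/0.0439 = 29%.

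**Other visit patterns, 66 encounters, patient term in both designs:**

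| Pattern | Variance at ICC 0.5, single pool / balanced | Excess at ICC 0.3, 0.5, 0.7 |
|---|---|---|
| 30 patients, half seen once (15×1, 7×2, 4×3, 1×4, 1×5, 2×8) | 0.0421 / 0.0349 | 14%, 21%, 27% |
| 15 patients (9×4, 6×5) | 0.0369 / 0.0308 | 15%, 20%, 23% |
| 7 patients (6×10, 1×6) | 0.0331 / 0.0303 | 8%, 9%, 10% |
| 30 patients (26×1, 4×10) | 0.0404 / 0.0377 | 6%, 7%, 8% |

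**Pairs needed.** Each patient with an odd number of visits leaves one envelope unused, so the number of pairs is (66 + odd-visit patients)/2. The even spread needs (66 + 6)/2 = 36 pairs. The most that 30 patients could need is (66 + 30)/2 = 48.

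**The case against.** The strongest reply is that the size of the loss rests on figures the plan does not give. A reader might infer that nearly half of the patients will receive one catheter. The documents do not support that as a fact: they never tie the 30 participants to the 66 encounters, and up to 10 participations are allowed. With 15 patients at four or five visits about 9% receive one catheter; with 7 patients near the cap, 0.4%. If visits are skewed over 30 patients the share rises to 65% or 87%, but mainly because many attend once, and no list can pair a single visit. All of this stands.

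A reader might also infer that the 66 encounters are worth only about 46 (66/1.42). That needs both the even spread and an ICC of 0.5. At ICC 0.1 the even-spread excess is 9%, and no ICC is given for any outcome.

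Nor does the text support calling the list unrestricted, since it is fixed at 33:33, or the comparison biased, since every encounter is still randomized. Under the single pool, the average variance of the plain group difference (about 0.060) is close to that for independent encounters (2/33 = 0.0606). As a pilot, the study also has no power target to miss.

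The plan does contain one within-patient element: each intervention participant's inlet rate is compared with the average of that patient's last five procedures. That comparison is historical and covers inlet rate only.

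Finally, pairing has a price. The second catheter of each pair is foreseeable; in the even spread that is 24 + 6 = 30 of 66 encounters. This stands and must be stated. What survives these objections is that the plan provides neither within-patient balance nor a patient term.

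**Conclusion.** The point holds as a loss of precision. It does not show bias or an invalid randomization. Under an even spread over 30 patients the patient-adjusted variance is about 9% to 57% larger than with within-patient balance, for ICC 0.1 to 0.7. At ICC 0.3 to 0.7 the excess is about 15% to 23% with 15 patients, and about 6% to 10% if a few patients near the cap supply most encounters. The link between 30 patients and 66 encounters, the spread of visits and the ICC are all assumptions. The firmest part is the missing patient term: adding it needs no change to the allocation and lowers the variance in every even-spread case shown. Balance within patient is a further gain whose size depends on how often patients return.

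**What to change.** 1. **Analysis.** Analyse all encounter outcomes with a patient term, for example a random intercept, and with procedure type. Both can be taken from the data collection form, which carries a patient sticker, a study number and the procedure type. The dataset must identify the patient as well as the encounter. The cost is a few sentences in the Statistical Analysis Plan. Without this term, balanced allocation would not show its benefit in the reported standard errors.

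2. **Allocation.** Give each patient's consecutive participating visits concealed pairs, one envelope per catheter in random order, with a new pair after every second visit. Prepare more than 33 pairs: 36 for the even spread, and 48 would cover any pattern over 30 patients. State what happens to unused envelopes, and accept that the final split may differ slightly from 33:33. With six half-used pairs, the difference between arms has a standard deviation of √6 = 2.4 encounters.

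3. **Downside to state.** Because the second catheter of a pair is foreseeable, log every eligible visit that is skipped, with the reason, and report the log.

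4. **Reconcile.** Potential Risks sends a patient back to randomization after a failed 20-gauge encounter, whereas a pair may already fix the next catheter. The protocol must say how the two rules fit together.

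The cost is extra envelopes, the log and a short amendment. No additional patients, procedures or blood samples are needed.

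### The PI is the only person declared blinded but also picks the envelope that discloses the group, so the stated single blinding is not delivered and the order of assignment is not protected

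*Combined protocol and SAP*

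**What the plan says.** **Blinding.** The Concise Summary of Project states: "It is a single blinded, randomized study". It does not say who is blinded. The Randomization Procedure section names one person: "The PI will be blinded, therefore the PI will pick an envelope when patients are consented and ready for treatment". Later in that section, on the envelope: "Inside the envelope it will tell the investigator if the patient is in the control or intervention group of the study".

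**Custody.** "The research coordinator will have 66 randomized envelops without replacement", half for each catheter. The numbers 1 to 66 were split at random between the groups, and "only the research coordinator will have access to the SID key" that links each study number to its group. The section calls this a backup to randomization. Allocation follows consent and is repeated at each encounter, with at most 10 encounters per patient.

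**Results and forms.** Under Study procedure, the plasma hemoglobin sample goes to the laboratory and "results will be sent back directly to the PI"; the PI or the study team enters the values in a spreadsheet. Sources of Research Material adds that results come through the patient's electronic record. The form in Appendix 1 has a catheter-type field on the same record as pain, inlet rate, return pressures, alarms and procedure time.

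**The concern.** A single-blind label tells readers that one party was kept from the allocation while outcomes were handled. Here the one party named is also the one who draws the allocation and receives an efficacy result. If the label cannot be supported, the trial is in effect open, and its results will be read with more confidence than they deserve.

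Envelope handling is a second, separate matter. If the person drawing can choose among envelopes, or if their order is not fixed, the link between random list and patient depends on good conduct alone. Every patient has a vein evaluation on referral, so the staff may already know which veins suit which catheter when the envelope is drawn.

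The trial aims to show equal efficacy, less pain and no more adverse events, and its data are meant to shape a full trial. A bias towards either catheter would carry forward into that design.

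**Working it through.** **1. Counts.** 66 / 2 = 33 envelopes per group, and 33 + 33 = 66, in agreement with the planned 33 encounters per group. The plan gives no significance level, power, effect size or standard deviation, so bias cannot be put on the scale of an endpoint.

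**2. Who is said to be blind.**
- PI: declared blinded.
- Treating nurse: starts the procedure with the assigned catheter and completes the form with its catheter-type field, so must know the group.
- Patient: no statement. The patient marks the pain scale on a form that also carries the catheter-type field, but nothing says whether the patient reads it or is told the gauge.
- Laboratory and analyst: no statement.

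The label therefore rests on the PI alone.

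**3. Can the PI stay blind?** The envelope text allows two readings.
- If the investigator who learns the group is the PI, blinding ends when the envelope is opened.
- If it is someone else, the protocol does not say who opens the envelope or how its content is kept from the PI who has just picked it.

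The wording of the PI sentence, in which picking follows from being blinded, suggests that the term means only not knowing the group before the draw. That is concealment of the next assignment, not blinding while outcomes are collected. No reading supplies the blinding that the summary claims.

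**4. Do later steps restore it?** The Statistical Analysis Plan has all data collected first on the form, so anyone who transcribes it sees the catheter type. Laboratory results arrive under the patient's identity, and Procedures to Maintain Confidentiality gives the PI access to the link between study number and name. Restricting the group key to the coordinator does not close these routes.

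**5. Envelope order.** Nothing says that the envelopes are sealed, opaque, sequentially numbered, used in fixed order or logged when opened. At a first visit, consent comes before the draw and gives some separation. At later visits there is no new consent. With the 30 participants expected in the recruitment section, all 66 encounters used and at least one encounter each, repeat draws number 66 − 30 = 36, and 36 / 66 = 55%. At the cap of 10 encounters, 66 / 10 = 6.6, so at least 7 participants are needed; then 66 − 7 = 59 draws (89%) are repeats.

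**6. Which outcomes are exposed.**
- The plasma hemoglobin value, one of the two efficacy measures, is a laboratory measurement. Knowledge of the group has limited scope to change it.
- Minutes to complete the procedure, the other efficacy measure, depend partly on how the nurse handles alarms.
- Pain is self-reported, and alarms are recorded by the nurse.
- No section says who records or judges adverse events.

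**The case against.** The strongest reply is that the text is loose but not shown to fail. The title page lists a co-investigator, so the investigator told the group need not be the PI. The coordinator holds a fixed stock of 66 envelopes, drawn without replacement, and a separate key. Receiving a laboratory result breaks no blind by itself. Figure 1 is not available here and may show more of the procedure.

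Much of this stands, and it rules out several stronger readings that a reader might infer.
- **That the envelopes are unnumbered.** The text does not say so; the numbers 1 to 66 and the key point the other way. What can be said is that numbering and fixed order are not stated.
- **That a re-draw would go undetected.** Coordinator custody and the key offer some check. How much is unclear: the confidentiality section gives study numbers to participants, while groups change by encounter.
- **That the PI scores hemolysis or adverse events.** No section names the scorer of either.
- **That the patient sees the gauge.** This is not stated; nor is the patient said to be masked.
- **That predictability measures the defect.** An observer who knows every earlier draw and always guesses the group with more envelopes left expects 33 + 2^65 / C(66,33) − 0.5 = 37.6 correct of 66 (57%), with the last 66 / 34 = 1.9 certain on average. This is true of any fixed 33:33 list seen by one observer. It depends neither on who draws nor on numbering, and the fix below does not change it.

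What the reply does not supply is any step that keeps the PI from the content of an envelope that the PI picks.

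**Conclusion.** The point holds and is wrong as written. The trial is labelled single blinded, the PI is the only person declared blinded, and the described conduct does not keep the PI blind. Separately, assignment order is not secured by any described safeguard; it is not shown to have been breached.

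The size cannot be given as bias in an endpoint. The exposure is that 36 of 66 draws would be repeat draws if 30 participants supply all the encounters, and that pain, alarms, adverse events and procedure time are more open to influence than plasma hemoglobin. The conclusion assumes that Figure 1 adds no safeguard absent from the text. No sample-size figure changes. This should be corrected before enrolment, or disclosed as a limitation if enrolment has begun.

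**What to change.** 1. Remove the envelope pick from the PI. Once the patient is consented and confirmed ready, the coordinator hands over the next sequentially numbered, sealed, opaque envelope and logs its number, date and time.
2. The treating nurse, who must know the group anyway, opens it. Neither the PI nor the key holder does. The key holder takes no part in deciding enrolment or readiness, because that person may know the next assignment.
3. The PI handles laboratory results by encounter code, without the catheter-type field, until data lock. Since results come through the patient's record, a study team member other than the PI must retrieve and code them. The existing route for passing abnormal results to clinical staff stays as it is.
4. Restate the blinding in the Concise Summary of Project: open to the treating nurse, PI blinded, and whether the patient is told the catheter type. If the PI cannot be kept from the allocation, call the trial open-label.

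The cost is protocol wording, numbering 66 envelopes, a log and a small coding task; no extra post is evident, provided that someone other than the key holder takes consent. The fix makes the PI's blinding real. It does not mask the nurse, so pain, alarms and procedure time should still be reported as collected with the group known at the bedside.
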